## 3.1.4.12 Time to First Rescue Treatment Recommendation through Week 28/Follow Up

Time to first rescue treatment recommendation will be counted from date of insertion procedure, i.e., date of first rescue treatment recommendation – date of LYR-220 administration/sham insertion procedure + 1. If a subject is lost to follow up/discontinues the study before Week 28/Follow Up and does not have rescue treatment requirement by that time, then it will be censored at the date of last assessment. If a subject does not have rescue treatment required through Week 28/Follow Up, it will be censored at Week 28/Follow Up.

# 3.1.4.13 Ethmoid Cavity Opacification by CT at Week 25/Follow Up

Ethmoid cavity opacification will be assessed by CT. The Screening CT should be performed anytime between the Screening and Day 1 visits. Alternatively, a historical CT scan can be used, if done within 3 months preceding the Screening visit. The follow-up CT will be conducted within 5-9 days after the LYR-220 removal procedure at Week 25/Follow Up visit. If a subject is experiencing or recovering from a cold, acute exacerbation of nasal allergy, or upper respiratory tract infection at the Week 25/Follow Up visit, the CT assessment should be performed 4 weeks after resolution of the adverse event. If a subject early terminates from the study or requires oral/systemic corticosteroids or sinonasal surgery as rescue treatment during the study, every attempt should be made to perform the follow-up CT before subject receives the rescue treatment. The percent opacification of ethmoid cavity will be evaluated by an imaging core lab.

Bilateral percent opacification of ethmoid cavity is the average of percent opacification of ethmoid cavity on each side of the nose.

## 3.1.4.14 PGIS at Week 8, 16, and 24

Responses to the PGIS questionnaire will be collected via the ePRO. Subjects will be asked a single question to rate their severity of CRS-related symptoms over the past 7 days on a 5-point ordinal scale: 1 = none, 2 = mild, 3 = moderate, 4 = severe, and 5 = very severe.

#### 3.1.4.15 PGIC at Week 24

Responses to the PGIC questionnaire will be collected at Week 24 via the ePRO. The PGIC is a self-assessment of the subject's overall change in CRS-related symptom severity compared to

pretreatment. The PGIC 7-point balanced scale is as follows: 1 = very much better, 2 = much better, 3 = a little better, 4 = no change, 5 = a little worse, 6 = much worse, and 7 = very much worse.

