8.4.2 Ethmoid Cavity Opacification Imaging

Ethmoid cavity opacification will be assessed by CT at the time points specified in the Schedule of Assessments (Section 8.1), unless medically contraindicated. The Screening CT should be performed anytime between the Screening and Day 1 visits. Alternatively, a historical CT scan can be used if done within 3 months preceding the Screening visit. The follow-up CT will be conducted within 5-9 days after the LYR-220 removal procedure at Week 25 visit. If a subject is experiencing or recovering from a cold, acute exacerbation of nasal allergy, or upper respiratory tract infection at the Week 25 visit, the CT assessment should be performed 4 weeks after resolution of the adverse event. If a subject early terminates from the study or requires SCS or sinonasal surgery as rescue treatment during the study, every attempt should be made to perform the follow-up CT before subject receives the rescue treatment. The percent opacification of ethmoid cavity will be evaluated by an imaging core lab.

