9.8.1.3 Oral Steroids or Sinonasal Surgery Recommendation

The endpoint will be summarized using the percentage of subjects being recommend by treating physician for oral/systemic steroids (SCS) or sinonasal surgery in each treatment group. Comparison between each LYR-220 group and the sham procedure group will be performed using a Cochran-Mantel-Haenszel (CMH) test controlling for nasal polyp status.

9.8.1.4 CFBL in Bilateral Percent Ethmoid Cavity Opacification by CT at Week 25

Mean CFBL in bilateral percent ethmoid cavity opacification by CT at Week 28 will be compared between each LYR-220 group and the sham procedure group using an ANCOVA model with fixed-effect terms for treatment group and nasal polyp status with baseline score as a covariate.

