### 3.1.1 Analysis Day

Analysis day for analysis visit windows (i.e., "Aday") will be calculated from the date of study treatment (LYR-220 or sham) administration. The day of study treatment administration will be Aday 1, and the day immediately before Aday 1 will be Aday -1.

Additionally, analysis day relative to the last dose day (i.e., "Aenday") will be calculated from the date of last dose of study treatment. The day of last dose of study treatment will be Aenday 0, and the day immediately after Aenday 0 will be Aenday 1. Data collected up to 31 days after end of treatment will be included in the analysis.

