## 3.1.2 Analysis Visits

Analysis visits will be used for efficacy and safety endpoint analysis. Follow up visits are defined as any visits during 1 day and up to 31 days after end of treatment. Scheduled visits will be assigned to analysis visits as recorded on the Case Report Form (CRF) if they are within the corresponding analysis visit windows described in the tables below. Scheduled visits that do not fall in the corresponding analysis visit windows are considered unscheduled visits when assigning analysis visits. In order to maximize the data available for assessments with regular scheduled visits, where possible, results from unscheduled visits will be assigned to analysis visits according to the following visit windows. When multiple visits are within the same analysis visit window, the one closest to the target day will be used. For efficacy endpoints, if two values are equally distanced, select the value before the target day.

If both paper-based patient-reported outcomes and ePRO are completed at the same day, ePRO will be used for analysis.

If multiple ePRO are completed at the same day and the input are different, the entry having the worst total score will be used for analysis. If multiple ePRO are completed at the same day and the input are identical, the earliest entry will be used for analysis.

An unscheduled visit that does not fall under any window will remain in the database and will be included in the listings.

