# **Table 1f. Visit Windows for Ethmoid Cavity Opacification**

Analysis Visit	Target Analysis Day	Low Analysis Day	High Analysis Day
Week 25/follow-up*	Aenday 7	Aenday 0	Aenday 31

\* post-treatment follow-up.

\* post-treatment follow-up.

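### The SAP's 31-day limit on follow-up CT data shuts out scans that the plan itself defers for an illness still present at the Week 25 visit

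*SAP*

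**What the plan says.** Protocol 8.4.2 sets the routine timing: "The follow-up CT will be conducted within 5-9 days after the LYR-220 removal procedure at Week 25 visit". SAP 3.1.4.13 repeats it. Both then give a deferral rule for a subject who has, or is getting over, a cold, a nasal allergy flare or an upper respiratory infection at the Week 25 visit: "the CT assessment should be performed 4 weeks after resolution of the adverse event". A footnote to the protocol's schedule of assessments says the same. None of the three gives a tolerance or a last day for the deferred scan.

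The SAP limits the data in three places:

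- "Table 1f. Visit Windows for Ethmoid Cavity Opacification" has one row, Week 25/follow-up, with target Aenday 7, low Aenday 0 and high Aenday 31. Aenday counts from the last dose of study treatment.
- SAP 3.1.1: "Data collected up to 31 days after end of treatment will be included in the analysis".
- SAP 3.1.2: "Follow up visits are defined as any visits during 1 day and up to 31 days after end of treatment".

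SAP 3.1.2 also says what happens to a scan outside the window: "Scheduled visits that do not fall in the corresponding analysis visit windows are considered unscheduled visits when assigning analysis visits", and then "An unscheduled visit that does not fall under any window will remain in the database and will be included in the listings". SAP 3.1.10.3.2 rules out imputation of a missing CT. Table 1f, 3.1.4.13 and the CT analysis in 3.4.2.7 contain no exception for a deferred CT.

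**The concern.** The deferral rule and the analysis window cannot both be met when the illness is still present at the Week 25 visit. Sites that follow the instruction produce a scan that the SAP then leaves out of the analysis.

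Two endpoints use this CT. The first is the Part 2 ANCOVA of change in bilateral percent ethmoid opacification. The second is the responder endpoint on no longer being a candidate for revision surgery (SAP 3.1.4.16). There the CT is decisive only for a subject without revision surgery whose Week 24 3CS score is above 4 or missing.

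Timing adds some weight. Under SAP 4.2, treatment allocation is unblinded at the primary lock, and later changes that affect the analysis count as post hoc. A decision to bring these scans back in would then be made with allocation known.

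**Working it through.** **The plan's own figure.** Aenday 31 is a stipulated limit, so there is nothing to recompute. It matches the top of the protocol's Week 28/EOS window, 25-31 days after EOT.

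**Inputs.**
- Window limit: Aenday 31 (SAP Table 1f).
- Week 25 visit: 5-9 days after removal (protocol 8.4.2, SAP 3.1.4.13).
- Deferral: 4 weeks after resolution (same sections), taken as 28 days with no tolerance. This is an assumption, because the text gives no tolerance.
- Aenday 0: SAP 3.1.1 defines it by the last dose. For a matrix inserted once, this is read as the removal day, which is also an assumption.

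**Earliest deferred scan.** Scan day = visit day + d + 28, where d is the number of days from the visit to resolution. The values 7 and 14 for d are assumed.
- d = 0: 5 + 28 = 33 to 9 + 28 = 37. Past the limit by 33 − 31 = 2 to 37 − 31 = 6 days.
- d = 7: 40 to 44, past by 9 to 13 days.
- d = 14: 47 to 51, past by 16 to 20 days.

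**Latest resolution that still fits.** 31 − 28 = Aenday 3, before the visit window opens on Aenday 5. A subject who is only recovering at the visit, and whose illness resolved by Aenday 3, can still be scanned in window. Resolution on Aenday 4 gives day 32, which is already outside.

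**Effect of a tolerance.** If the scan could be taken 3 days early (assumed), the latest resolution that fits is 31 − 25 = Aenday 6. That rescues only visits on Aenday 5 or 6 where the illness clears on the visit day or, for a visit on Aenday 5, the day after.

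**Bilateral dislodgement.** Protocol 4.1.2 allows up to 7 days from the second dislodgement to the ET visit, and 5-9 days more to the Week 25 assessments. If Aenday 0 is the dislodgement day, the visit falls on about 0 + 5 = 5 to 7 + 9 = 16. The earliest deferred scan is then day 33 to 44, past the limit by 2 to 13 days.

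**Against the final lock.** SAP 4.3 ties the final lock to completion of Week 28. The deferred scan comes 33 − 31 = 2 to 37 − 25 = 12 days after the subject's own Week 28 visit if d = 0, and 47 − 31 = 16 to 51 − 25 = 26 days after it if d = 14.

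**Cost in precision.** The documents give no illness rate. Assuming 2.5%, 5% and 10% of the 40 Part 2 subjects gives 1, 2 and 4 lost scans. The SE ratio is √(1/n₁ + 1/n₂) / √(1/20 + 1/20), with equal residual variance:
- 19 and 20: 1.013 (+1.3%)
- 19 and 19: 1.026 (+2.6%)
- 18 and 18: 1.054 (+5.4%)

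**The case against.** The strongest reply is that a limit at day 31 is a reasonable choice for the main analysis. A scan at day 33-51 measures the cavity about 5 to 7 weeks after the drug is removed, not about 1 week after. Keeping the limit and using late scans only for sensitivity could be defended. The difference in timing is real and has to be stated. But SAP 3.1.4.13 puts the deferral rule inside the definition of the Week 25/Follow Up CT endpoint, so the plan treats the deferred scan as that endpoint's value. If the limit was meant to override it, the SAP should say so.

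The second reply is that the arithmetic assumes exactly 28 days and removal as day 0. This is correct. As shown above, a 3-day tolerance rescues only a few cases, and dating from dislodgement can only lengthen the overrun.

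The third reply is that the number affected may be zero. That stands, and it keeps the point minor.

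A reader might infer from protocol 9.8.1.4 that the CT analysis has no upper day limit. The text does not show this: "Mean CFBL in bilateral percent ethmoid cavity opacification by CT" is followed by a reference to Week 28, under a heading that says Week 25. The section is inconsistent on the timepoint and supports neither side.

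A reader might also infer that subjects rescued with systemic steroids lose their CT value, because a scan taken before rescue falls outside the window. The documents do not support that either. The Week 25 CT is scheduled for all subjects, and SAP 3.1.2 with Table 1f selects the in-window scan.

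**Conclusion.** The conflict is real and narrow. On the stated assumptions, a follow-up CT deferred for an illness unresolved at the Week 25 visit cannot fall inside Table 1f. As the SAP is written, the scan is listed and not analysed. It does not follow that every deferred CT is lost, since an illness over by Aenday 3 still fits. Nor do the documents show that losses would differ between arms.

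The size is minor. CT is one of 11 secondary efficacy endpoints in SAP 2.3.3, with no multiplicity adjustment, in a study not sized on power. It is not among the primary-lock outputs, and the team cleaning data for the final lock does not receive the detailed patient-level results. The number of subjects affected cannot be derived from the documents, and the precision figures rest on assumed losses.

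**What to change.** Make these changes before the primary lock unblinds treatment:

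- Add a CT-only exception to Table 1f, SAP 3.1.1 and the follow-up visit definition in SAP 3.1.2. A CT documented as deferred under the illness rule counts as the Week 25/Follow Up value for both the ANCOVA and the responder endpoint.
- Amend SAP 4.3 so that the final lock waits for outstanding deferred CTs, or state a last acceptable day for them. Without this, deferred scans from the last subjects enrolled could still be lost.
- List actual scan days, and repeat the ANCOVA without deferred scans as a sensitivity analysis.

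Leave the laboratory, slit-lamp, endoscopy, IOP and adverse event limits as they are, and do not change the clinical timing rules.

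The cost is a table footnote, a few sentences and some programming. There are two downsides. CT timing becomes more mixed, with deferred scans about 5 to 7 weeks or more after removal instead of about 1 week. The final lock may also move: on the figures above, a deferred scan comes 2-12 days after the subject's Week 28 visit if the illness resolves on the visit day, and 16-26 days after it if resolution takes an assumed 14 days more.

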#### 3.1.4.16 No longer a candidate for revision surgery

Subjects will be deemed as having converted if they do not undergo revision sinonasal surgery (planned or actual) during the study and if they meet the following criteria:

- 3CS score ≤4 at Week 24, or
- No disease in ethmoid cavities on Week 25/Follow Up CT.

# 3.1.4.17 Nasal Inflammatory Marker Levels

Nasal inflammatory marker levels will be assessed by collecting nasal swabs. The baseline nasal swabs will be collected before LYR-220 administration at Day 1 visit. The follow-up nasal swabs will be collected at Week 25/Follow Up visit. Nasal swabs will be collected from each side nasal passage to assess levels of T2 inflammatory markers. Two nasal swabs per side (1 for protein sample collection and 1 for RNA sample collection) will be collected. Nasal swabs will be collected according to the guidelines provided by the Sponsor.

# 3.1.5 Summary Statistics

Categorical data will generally be summarized with counts and percentages of subjects. The denominator used for the percentage calculation will be clearly defined. Quantitative data will generally be summarized with descriptive statistics including n (number of non-missing values), mean, median, standard deviation (SD), minimum, and maximum.

#### 3.1.6 Hypothesis Testing

No hypothesis testing will be performed for Part 1.

For Part 2, unless stated otherwise, tests will be carried out on one-sided. Two-sided equitailed 90% (asymptotic) confidence intervals (CIs) will also be calculated.

# 3.1.7 Multiplicity

There will be no adjustment of the significance level for multiple comparisons across the endpoints.

#### 3.1.8 Adjustment for Covariates

Unless otherwise noted, all analyses of efficacy outcome measures will include subject's baseline score as a covariate and nasal polyp status (yes or no) as a factor in the analysis model.

## 3.1.9 Evaluation of Site Effect

The number of subjects at each site is expected to be too small to evaluate site effect. No site effect will be evaluated in this study.

- 3.1.10 Handling of Dropouts and Missing Data
- 3.1.10.1 Handling of Partial or Missing Dates for Prior and Concomitant Medications

The goal for imputing a partially missing date is to select the most conservative date within the possible range specified by the non-missing data.

Table 5. Imputation Rules for Missing Date

Date	Type of Missing Date	Handling of Missing Date
Event Start Date	Completely missing	No imputation will be applied.
(e.g., YYYY-MM-DD)	Only YYYY is available	Use the first day of YYYY to impute the missing month and date parts of the start date.
	YYYY and MM are available, but DD is missing	Use the first day of MM to impute the missing date part of the start date.
Event End Date (e.g., YYYY-MM-DD)	Completely missing	No imputation will be applied.  The event will be considered ongoing at the end of study.
	Only YYYY is available	Use the last day of YYYY to impute the missing month and date parts of the end date
	YYYY and MM are available, but DD is missing	Use the last day of MM to impute the missing date part of the end date

In the case where the imputed start date is later than the reported stop date, the imputed date will be set equal to the stop date.

In listings, missing or partial dates will be left as they have been recorded in the eCRF.

3.1.10.2 Algorithm for Treatment Emergent Adverse Events (TEAE)

TEAE is defined in Section 3.6.1.

For deriving the TEAE flag, the following process of temporary date imputation is done for adverse event (AE) start date. The date imputation algorithm for incomplete adverse event start dates is described in the following table. Classification of adverse event (TEAE or not) is then done using the imputed date.

In the following table, all dates are presented using an YYYY-MM-DD format. As an example, suppose the investigational medicinal product (IMP) administration = 2022-08-11 and several AEs have incomplete start dates.

Table 6. Imputation Rules for Missing AE start Date

Description of incomplete date   Imputed nume		Example	
	date	Character date	Imputed date
Day is missing			
YYYY-MM < YYYY-MM of [IMP	YYYY-MM-01	2022-07-XX	2022-07-01
admin.]			

YYYY-MM = YYYY-MM of [IMP	Min ([IMP admin.],	2022-08-XX	Min (2022-08-
admin.]	AE end date)		11, AE end date)
YYYY-MM > YYYY-MM of [IMP	YYYY-MM-01	2022-09-XX	2022-09-01
admin.]			
Day and month are missing			
YYYY < YYYY OF [IMP admin.]	YYYY-01-01	2021-XX-XX	2021-01-01
YYYY = YYYY OF [IMP admin.]	Min ([IMP admin.],	2022-XX-XX	Min (2022-08-
	AE end date)		11, AE end date)
YYYY > YYYY OF [IMP admin.]	YYYY-01-01	2023-XX-XX	2023-01-01
Day, month, and year are missing			
XXXX-XX-XX	Min ([IMP admin.],		Min (2022-08-
	AE end date)		11, AE end date)

YYYY = non-missing year, MM = non-missing month, DD = non-missing day, XX = missing field.

Actual data values as they appear in the original eCRFs will be presented in the data listings.

3.1.10.3 Handling of Missing Data and Data Post-Rescue Treatment for Efficacy Endpoints 3.1.10.3.1 Part 1

No imputation will be performed. All efficacy data will be summarized descriptively.

#### 3.1.10.3.2 Part 2

The details for handling missing data and intercurrent events for the secondary efficacy endpoints are specified in the estimand framework in Section 3.4.2. There will be no imputation for missing bilateral percent ethmoid cavity opacification by CT or nasal inflammatory biomarker assessments.

#### 3.1.10.4 Handling of Missing Data for PK

Missing data handling for PK are specified in Section 3.5.2.

#### 3.2 Analysis Sets

See Section 3.1 General Considerations for handling the subjects from Part 1 and Part 2.

#### 3.2.1 Safety Analysis Set

The safety analysis set is defined as subjects who successfully received the study treatment on Day 1. Subjects will be analyzed according to the treatment received. This is the primary analysis set for assessment of safety. The subjects from Part 1 will be combined with the subjects from Part 2 (see Section 3.1).

#### 3.2.2 Efficacy Analysis Set

The efficacy analysis set is defined as subjects who successfully received the study treatment on Day 1. This is the primary analysis set for assessment of efficacy. Subjects will be analyzed according to the planned/randomized treatment. The subjects from Part 1 and the subjects from Part 2 will be separated (see Section 3.1).

## 3.2.3 PK Analysis Set

The PK analysis set is defined as subjects who receive at least one dose of study drug and have at least one measured concentration.

#### 3.3 Subject Data and Study Conduct

Data will be listed by site and subject.

#### 3.3.1 Screening

The number and percentage of subjects in each of the following categories will be presented in total for all consented subjects:

- Screened,
- Screen failure.
- Primary reason for screen failure,
- Enrolled and successfully received the study treatment on Day 1 in Part 1,
- Randomized and successfully received the study treatment on Day 1 in Part 2.

In addition, the number and percentage of subjects who screen failed due to COVID-19 will also be presented.

## 3.3.2 Subject Disposition

The number and percentage of subjects in each of the following categories will be presented by treatment and in total for the Safety Analysis Set as well as for the Efficacy Analysis Set in Part 2:

- Successfully completed bilateral insertion procedure on Day 1,
- · Completed the treatment,
- Completed the study,
- · Early terminated the study treatment,
- Early terminated the study,
- Primary reasons for discontinuation of study treatment,
- Primary reasons for discontinuation of study.

In addition, the number and percentage of subjects who discontinued study treatment due to COVID-19 and discontinued the study due to COVID-19 will also be presented.

#### 3.3.3 Protocol Deviations

Counts and percentages of subjects with CSR-reportable protocol deviations by deviation category will be summarized by treatment and in total for the Safety Analysis Set as well as for the Efficacy Analysis Set in Part 2.

## 3.3.4 Demographic and Baseline Characteristics

The following demographic and baseline characteristics will be summarized:

- Age (years) and age categories (<65 years, ≥65 years)

- Sex
- Childbearing potential

- Race
- Ethnicity
- Height (cm)
- Weight (kg)
- Body mass index (BMI) (kg/m²) and BMI categories (<30 kg/m², ≥30 kg/m²)

- Geologic category (United States, Australia)
- Randomized stratum (with or without nasal polys, only for randomized subjects in Part 2)
- Actual stratum (with or without nasal polys, only for randomized subjects in Part 2)

Demographic and baseline characteristics will be summarized with descriptive statistics or counts and percentages of subjects as appropriate by treatment and in total for the Safety Analysis Set as well as for the Efficacy Analysis Set in Part 2.

